### **2.9.3.2 Renal events**

Summary table and listing will be presented for “renal event overview”. In addition, individual subject data listings will be presented for renal event imaging, pathology, renal function and urinalysis.

## **2.9.4 Other safety data**

### **2.9.4.1 ECG and cardiac imaging data**

The following quantitative variables may be summarized if requested: ventricular rate, RR interval, PR interval, QRS duration, QT interval, and corrected QT interval (QTc). Both Bazett (QTcB) and Fridericia (QTcF) corrections will be presented for QTc.

Notably abnormal ECG parameters post-baseline will be summarized by computing the number and percentage of subjects with:

- QTcF > 500 msec
- QTcF > 480 msec
- QTcF > 450 msec
- QTcF changes from baseline > 30 msec
- QTcF changes from baseline > 60 msec
- PR > 250 msec

A by-subject listing of all quantitative ECG parameters will be provided.

### **2.9.4.2 Vital signs**

Analysis in vital sign measurements using descriptive summary statistics for the change from baseline for each post-baseline visit will be performed by vital sign and treatment group. Change from baseline will only be summarized for subjects with both baseline and post-baseline values and will be calculated as:

$$\text{change from baseline} = \text{post-baseline value} - \text{baseline value}$$

Only “on-treatment” vital signs will be summarized (i.e. assessments within last dose plus 84 days) by treatment groups for induction, maintenance and extension periods. All vital signs will be listed with “on-treatment” flag displayed.

[figure not shown]
The number and percentage of subjects with newly occurring notable vital signs will be presented for induction, maintenance up to week 52 and entire treatment periods by treatment

group. Subjects not meeting the following criteria at baseline but meeting at post-baseline will be considered to be subjects with newly occurring abnormalities. Criteria for notable vital sign abnormalities are provided in [Table 2-15](#) below.

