### 6.5.3 Vital signs

Vital signs (including blood pressure and pulse measurements) will be assessed at every scheduled visit as indicated in [Table 6-1](#), [Table 6-2](#). If possible, assessments should be performed by the same study site staff member throughout the study.

After the subject has been sitting for five minutes, with back supported and both feet placed on the floor, systolic and diastolic **blood pressure will be measured twice** (measurements separated by 1 to 2 minutes) using a validated device, with a cuff that is appropriately sized for the subject's arm circumference. The average of the two measurements will be entered on the Vital Signs eCRF.

Whether action needs to be taken to address notable vital signs will be decided by the investigator/qualified site staff, taking into account the overall status of the subject. No specific action is foreseen as part of the study protocol. Notable values for vital signs are indicated in [Appendix 1, Table 13-1](#).

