## **Vital signs**

Analysis of the vital sign measurements using summary statistics for the change from baseline for each post-baseline visit will be performed. These descriptive summaries will be presented

by vital sign and treatment group. Change from baseline will only be summarized for subjects with both baseline and post-baseline values.

All information collected will be listed by patient and abnormal values (see [Appendix 1](#)) will be flagged.

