## 13 Appendix 1: Clinically notable laboratory values and vital signs

The following criteria will be used to define expanded limits and notable abnormalities of key laboratory tests and vital sign parameters.

Unless otherwise indicated (e.g. liver and renal safety monitoring procedure, [Section 7.3](#) and [Section 7.4](#) respectively) no specific action is pre-defined within this protocol to respond to specific abnormal laboratory values, as it will be decided by the investigator whether & which specific action needs to be taken to respond to any abnormal values, taking into account the overall status of the subject.

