## **Vital Signs**

The following notable criteria will be used for systolic and diastolic BP and pulse. The age indicated is the age at the time of the visit.

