**Table 13-1 Notable Pediatric ranges for vital signs\***

Age	Systolic BP	Diastolic BP	Pulse (BPM)
6 yrs	91-125	53-84	60-130
7 yrs	92-126	55-86	60-130
8 yrs	94-127	56-88	60-130
9 yrs	95-129	57-89	60-110
10 yrs	97-130	58-90	60-110
11 yrs	99-132	59-90	60-110
12 yrs	101-135	59-91	60-110
13 yrs	104-137	60-91	60-110
14 yrs	106-140	60-92	60-110
15 yrs	107-142	61-93	60-110
16 yrs	108-145	63-94	60-110
17 yrs	108-147	64-97	60-100
18 yrs	-	-	60-100

Source: <http://www.who.int/childgrowth/standards>

\*values outside the provided ranges are considered notable

The Recommendations for the dimensions of Blood Pressure Cuff Bladders are noted in the following table.

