**Table 2-3 Rules for selecting values for analysis**

| Timing of measurement  | Type of data                                    | Rule  |
|------------------------|---|---|
| Baseline               | All data  | See Section 2.1.1.3   |
| Post-baseline efficacy | All data except CDLQI, CHAQ                     | 
The measurement closest to the target day will be used. In the event two measurements are taken equally apart (e.g., 1 day before target date and 1 day after), then the earlier one will be used.
 
If two measurements are taken on the same day, then the first one using eCRF visit number.
 
If two measurements have been taken on the same day and same visit, then the worst measurement will be used.
   |
| Post-baseline efficacy | CDLQI, CHAQ                                     | 
The measurement closest to the target day will be used. In the event two measurements are taken equally apart then the earlier one will be used. If two measurements are taken on the same day, the worst measurement will be used.
 
If two measurements have the same value, select then the first one using eCRF visit number.
   |
| Post-baseline safety   | Summary visit information (e.g. lab, ECG, etc.) | 
The (non-missing) measurement closest to the target day will be used.
 
In the event two measurements are taken equally apart (e.g. 1 day before target date and 1 day after), the first one will be used.
 
If two measurements are taken on the same day, then the first one will be used (using the time).
 
If two measurements are taken on the same date/time, then the first visit number will be used (assuming this is the planned visit).
 
If two measurements are taken on the same date/time/eCRF visit number, then the average value of these two results will be used.
 |

|                      |  |   |
|----------------------|--|---|
| Post-baseline safety | Notable abnormalities (e.g. vital signs) and CTCAE grading for laboratory values | The most extreme measurement in the window will be used. Note this means a subject can have a notably high and notably low measurement within a window. |
|----------------------|--|---|

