**Table 2-15 Criteria for notable vital sign for pediatric patients**

| Age group | Systolic BP(mmHg) | Diastolic BP(mmHg) | Pulse (bpm) |
|------------------|--------------------------|---------------------------|--------------------|
| 6 -11 yrs        | 90-130                   | 50-80                     | 50-105             |
| 12-17 yrs        | 90-145                   | 55-90                     | 45-95              |
| 18 yrs and over  | 90-140                   | 60-90                     | 60-100             |

Data of subjects with newly occurring notable vital signs abnormalities will be listed in an additional listing.

[figure not shown]

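### SAP Table 2-15 and protocol Table 13-1 set different limits for notable vital signs (70 of 72 differ, in both directions), SAP Section 4 does not declare the change, and the SAP counting sentence reads backwards

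*SAP*

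**What the plan says.** **Protocol.** Appendix 1 opens by saying "The following criteria will be used to define expanded limits and notable abnormalities of key laboratory tests and vital sign parameters". Its vital-signs paragraph adds "The following notable criteria will be used for systolic and diastolic BP and pulse", with age taken at the time of the visit. Table 13-1 then gives a range for systolic pressure, diastolic pressure and pulse at each year of age, with the footnote that "values outside the provided ranges are considered notable". Section 6.5.3 sends investigators to the same table ("Notable values for vital signs are indicated in" Appendix 1). In Section 9.5.3 the vital-signs analysis says "All information collected will be listed by patient and abnormal values" under Appendix 1 will be flagged.

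**SAP.** Section 2.9.4.2 tabulates subjects with newly occurring notable vital signs for induction, maintenance up to Week 52 and the entire treatment period. The rule is "Subjects not meeting the following criteria at baseline but meeting at post-baseline will be considered to be subjects with newly occurring abnormalities". The criteria are those of Table 2-15, titled "Criteria for notable vital sign for pediatric patients", which lists plain ranges for ages 6–11, 12–17, and 18 and over, with no note that values outside them are the notable ones. Table 2-3, on selecting values within a visit window, says "Note this means a subject can have a notably high and notably low measurement within a window".

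**Record of the change.** The SAP document history for 27 March 2019, before the Week 24 database lock, notes an update to the vital-sign criteria in Section 2.9.4.2. Section 4, which lists changes to protocol-specified analyses, does not mention it.

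**The concern.** The two documents define the same term differently. A programmer following the SAP and a reader following the protocol would flag different readings in the same child. The discrepancy does not run one way, so neither table can be called the more cautious one. Vital signs are part of the stated safety and tolerability objective, and the newly notable counts are the SAP's categorical summary of them.

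The counting sentence is a separate fault. The criteria in Table 2-15 are intervals of acceptable values. Taken literally, a subject who moves into the interval is newly abnormal and one who moves out of it is not.

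**Working it through.** **Inputs.** Protocol Table 13-1, ages 6 to 17: 12 ages × 3 signs × 2 limits = 72 limits. Each was compared with the SAP Table 2-15 limit for the band containing that age:

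| SAP band | Systolic | Diastolic | Pulse |
|---|---|---|---|
| 6–11 years | 90–130 | 50–80 | 50–105 |
| 12–17 years | 90–145 | 55–90 | 45–95 |

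Both tables were read as outside the range = notable. A lower limit is tighter if it is higher, and an upper limit is tighter if it is lower.

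**Count.** Two limits agree: systolic upper at age 10 (130) and at age 16 (145). So 72 − 2 = 70 differ.

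| Limit | Protocol tighter | SAP tighter | Equal |
|---|---|---|---|
| Systolic lower | 12 | 0 | 0 |
| Systolic upper | 8 (ages 6–9, 12–15) | 2 (ages 11, 17) | 2 |
| Diastolic lower | 12 | 0 | 0 |
| Diastolic upper | 0 | 12 | 0 |
| Pulse lower | 12 | 0 | 0 |
| Pulse upper | 0 | 12 | 0 |
| **Total** | **44** | **26** | **2** |

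The protocol therefore flags more low readings for all three signs. The SAP flags more high diastolic and high pulse readings.

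**Size of the gaps.** Of the 70 differences, 27 are 5 units or fewer, and 8 of those are 2 units or fewer. The largest is 25 beats per minute (pulse upper limit at ages 6–8: 130 in the protocol, 105 in the SAP).

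**Readings that change status (whole numbers).**
- Pulse, notable only under the protocol: 50–59 at ages 6–11; 45–59 at ages 12–17.
- Pulse, notable only under the SAP: 106–130 at ages 6–8; 106–110 at ages 9–11; 96–110 at ages 12–16; 96–100 at age 17.
- Systolic at age 15: 90–106 and 143–145 only under the protocol.
- Diastolic at age 10: 50–57 only under the protocol; 81–90 only under the SAP.

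**Age 18.** The pulse range is 60–100 in both tables. Table 13-1 gives no blood pressure limits, while Table 2-15 gives 90–140 and 60–90. Adding the two pulse limits makes it 70 of 74 comparable limits.

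**Counting sentence, read literally.** Take a 9-year-old, SAP systolic range 90–130. Going from 135 at baseline to 110 afterwards is not meeting then meeting the range, so it counts as newly abnormal. Going from 110 to 135 does not count. Both results are the reverse of what is intended.

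**The case against.** Four points can be made for the plan.

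- **Intent.** Meeting criteria for an abnormality plainly means being abnormal, and no programmer would flag a systolic pressure of 110 in a 9-year-old. This stands as to intent: Table 2-3 and the protocol footnote settle it. The sentence and the table still need correcting, but as a drafting matter.
- **The headline count.** Replacing yearly limits by bands makes most limits unequal by construction, and over a third of the gaps are 5 units or fewer. The count does measure disagreement and not impact. Banding does not explain all of it, though: the protocol pulse range is 60–110 at every age from 12 to 16, and the SAP replaces it with 45–95.
- **Disclosure.** The protocol's vital-signs analysis asks for flags in a listing and does not specify a table of newly notable values, so the count is largely a SAP addition. The criteria update is openly logged before the Week 24 lock, and nothing suggests it was driven by data. Both statements are correct. However, the log entry gives no reason and does not say that the limits depart from Appendix 1, which the protocol says will be used.
- **Consequence.** No hypothesis, alpha, sample size or protocol action depends on these flags. That also stands, and it limits the importance of the point without removing the contradiction.

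**Conclusion.** The concern holds. As written, the two documents give different notable flags, and hence different newly notable counts, for the same readings. For ages 6 to 17 they differ at 70 of 72 limits, 44 tighter in the protocol and 26 tighter in the SAP. The change is not declared in SAP Section 4 and no reason is given. The inverted counting sentence is a drafting error and not the intended rule. The SAP also omits the statement that age is taken at the visit, although its 18-and-over row implies it.

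The effect is confined to descriptive safety counts and flags. Efficacy analyses and change-from-baseline summaries are untouched, and all readings are listed and can be re-flagged. The limit counts rest only on reading both tables as outside the range = notable. The number of subjects affected is unknown. This should be corrected, but it does not threaten the trial's main conclusions.

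**What to change.** 1. Reconcile Tables 13-1 and 2-15 to one set of limits, including blood pressure at 18 and over. Which limits those should be is for the sponsor to decide.
2. If the SAP limits are kept, list the change and its reason in Section 4 and align protocol Appendix 1.
3. Retitle or footnote Table 2-15 to say that values outside the ranges are notable and that age is taken at the visit.
4. Reword Section 2.9.4.2 along these lines: a subject is newly notable high if not above the upper limit at baseline and above it at any on-treatment post-baseline assessment; newly notable low is defined in the same way against the lower limit. Treating high and low separately follows Table 2-3. The SAP's existing restriction of safety tables to planned visits (Section 2.9) still applies and should be read with this rule.

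The cost is two sentences, a table title, one Section 4 entry and a check of the limits lookup in the safety program.

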**Table 2-15 Criteria for notable vital sign for pediatric patients**

| Age group | Systolic BP(mmHg) | Diastolic BP(mmHg) | Pulse (bpm) |
|------------------|--------------------------|---------------------------|--------------------|
| 6 -11 yrs        | 90-130                   | 50-80                     | 50-105             |
| 12-17 yrs        | 90-145                   | 55-90                     | 45-95              |
| 18 yrs and over  | 90-140                   | 60-90                     | 60-100             |

Data of subjects with newly occurring notable vital signs abnormalities will be listed in an additional listing.

[figure not shown]

## 2.11 Pharmacogenetics

Not applicable.

## 2.12 PD and PK/PD analyses

Not applicable.

## 2.14 Growth and Physical development

Body weight, height and BMI percentile will be summarized by treatment and visit.

Standard height, weight, and BMI curves will be obtained from the U.S. National Center of Health Statistics ([www.cdc.gov/growthcharts](http://www.cdc.gov/growthcharts)) curves for ages up to 18 years. These growth curves will be used for all study subjects. The Center's files contain the L, M, and SD parameters needed to generate exact percentiles as follows:

$$z = \frac{\left(\frac{X}{M}\right)^L - 1}{L \times SD}$$

where X = physical measurement (e.g., patient's weight, height, and BMI)

M = median

SD= standard deviation

L = the power in the Box-Cox transformation

Percentiles for each patient at each time point will be calculated using the SAS function PROBNORM(z).

The number and percentages of subjects falling in low (i.e. <5), normal (i.e. 5-<95), or high (i.e. >= 95) growth percentiles will be summarized by treatment and visit. Shift from baseline

in growth percentile categories, i.e., low (i.e. <5), normal (i.e. 5-<95), or high (i.e.  $\geq 95$ ), will be summarized by treatment and visit for induction, maintenance and extension period.

## 2.15 Patient-reported outcomes

The impact of psoriasis on various aspects of subject's health-related quality of life (HRQoL) will be assessed by Children's Dermatology Life Quality Index (CDLQI).

The impact of Psoriatic Arthritis, on those subjects who have reported History of Psoriatic Arthritis will be assessed by their parent/custodian via the use of the childhood health assessment questionnaire, CHAQ®.

Completed questionnaires will be reviewed and examined by the site staff (not the investigator or evaluator of the subject for the physician assessments), before the clinical examination, for responses that may indicate potential AEs or SAEs. If AEs or SAEs are confirmed, then the events will need to be recorded as per instructions given in Section 7 of the protocol.

### 2.15.1 Children's Quality of Life Index (CDLQI)

The Children's Dermatology Life Quality Index ([Lewis-Jones and Finlay, 1995](#)) is a 10-item general dermatology disability index designed to assess health-related quality of life in pediatric subjects aged 4 to 16 years. It is self-explanatory and may be completed by the child with assistance from parents or caregivers as necessary.

The 10 questions cover six areas of daily activities including symptoms and feelings, leisure, school or holidays, personal relationships, sleep and treatment. The questions are based on the preceding week to permit accurate recall.

Each question is answered on a 4-point Likert scale scored from 0 to 3. These are added to give a minimum score of 0 and maximum score of 30. A higher CDLQI score indicated greater degree of QoL impairment. CDLQI is available in two versions, text only and text with cartoons. The text only version will be used in this study. The mean completion time of the text version is 120 seconds. The purpose of the CDLQI in this study is to investigate the effects of treatment of secukinumab with respect to CDLQI at Week 12, compared to placebo, and over time up to Week 52. This questionnaire should be completed in the language the subject is most familiar with before any other clinical assessments. The questionnaire should be completed by the subject with the help of parent/custodian if and as needed. The site staff may help understand the questions, as necessary. The subject should be given sufficient space and time to complete the questionnaire. The study coordinator should check the questionnaire for completeness and encourage the subject to complete any missing responses before the clinical examination. The CDLQI questionnaire will be completed by the subject.

For each of the seven scores, the percentage change from baseline will be derived. Summary statistics will be provided for absolute values as well as for the percentage change by visit and treatment group. The summary statistics will be presented for subjects till age  $<18$  years and a figure of change from baseline in CDLQI total score over time will be provided. An additional report will be created which will include only CDLQI assessments performed by subjects who were  $<16$  years of age at time of assessment.

CDLQI 0 or 1 achievement will be also analyzed by visit and over time until week 104 as previously specified in [Section 2.7.3](#).

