### **2.2 Secondary objectives**

- To demonstrate superiority of secukinumab (low and high dose) in subjects with severe chronic plaque psoriasis with respect to PASI 90 response at Week 12, compared to placebo.
- To assess efficacy of secukinumab in subjects with severe chronic plaques psoriasis with respect to PASI 50 and PASI 100 at Week 12, compared to placebo.
- To assess efficacy of secukinumab in subjects with severe chronic plaque psoriasis with respect to PASI 50, PASI 75, PASI 90 , PASI 100 and IGA mod 2011 0 or 1 at Week 16 and over time up to Week 52.
- To assess the efficacy of secukinumab with respect to changes in PASI score and IGA mod 2011 score at Week 12, compared to placebo, and over time up to Week 52.
- To investigate the effects of treatment with secukinumab with respect to changes in CDLQI at Week 12, compared to placebo, and over time up to Week 52.
- To investigate the effects of treatment of secukinumab with respect to CDLQI 0 or 1 achievement at Week 12, compared to placebo, and over time up to Week 52.
- To evaluate the effects of treatment of secukinumab on disability at Week 12 and over time up to Week 52 by use of the Childhood Health Assessment Questionnaire (CHAQ®), for subjects with history of psoriatic arthritis.
- To investigate the clinical safety and tolerability of secukinumab as assessed by growth, weight gain, tolerability of s.c. injections, vital signs, clinical laboratory variables, ECGs, and adverse events monitoring, compared to placebo.

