 If the first QuantiFERON® TB-Gold In-Tube test is indeterminate, the investigator may choose to perform a second QuantiFERON® TB-Gold In-Tube test (as part of an unscheduled visit) or refer the subject for tuberculosis workup per local guidelines. If the result of any QuantiFERON® TB-Gold In-Tube test is "positive" or the results of 2 sequential QuantiFERON® TB-Gold In-Tube tests are "indeterminate", the subject must be referred to have a tuberculosis workup per local guidelines (if no workup within 12 weeks prior to randomization is available). The subject will not be eligible for randomization if "active tuberculosis is present "or if "latent tuberculosis is present and is untreated as per local guidelines." No QuantiFERON® TB-Gold In-Tube test is to be done at the central laboratory after the subject has been randomized.

 Serum pregnancy tests will be performed at screening and urine pregnancy test at all other scheduled visits. If there is a positive urine pregnancy test, study treatment must be withheld and a serum pregnancy test done at the same visit. Pregnancy tests will be performed in female subjects of child bearing potential, i.e. those who have started menstruation and/or are of age 12 or older.

 Optional assessment. Chest X-ray or chest MRI (at prespecified sites) may be performed based on the investigator's judgment, to assess presence of infections or malignancies.

[REDACTED]

 Text only version will be used in all subjects. Assessment will no longer be performed once subjects reach 18 years of age.

 At visit 2 the PASI Score and BSA must be calculated by efficacy assessor/appropriate site staff prior to contacting IRT. The investigator must ensure subject meets all eligibility criteria before contacting IRT to randomize the subject. At Visit 8 (week12), the site should have the PASI 75 responder status calculated prior to contacting IRT to communicate it.

 For every visit (including unscheduled), weight measured at that visit will be entered into IRT.

 Etanercept will be administered weekly up to and including Week 51. Outside of site visits, administration should preferable occur at home by subject, or caregiver. Alternatively if subject/parent does not feel confident in performing study treatment administration at home, they are allowed to receive study treatment administration at site.

[REDACTED]

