#### **6.6.1.1 Children's Quality of Life Index (CDLQI)**

The Children's Dermatology Life Quality Index ([Lewis Jones and Finlay, 1995](#)) is a 10-item general dermatology disability index designed to assess health-related quality of life in pediatric subjects aged 4 to 16 years. It is self-explanatory and may be completed by the child with assistance from parents or caregivers as necessary. The 10 questions cover six areas of daily activities including symptoms and feelings, leisure, school or holidays, personal relationships, sleep and treatment. The questions are based on the preceding week to permit accurate recall.

Each question is answered on a 4-point Likert scale scored from 0 to 3. These are added to give a minimum score of 0 and maximum score of 30. A higher CDLQI score indicated greater degree of QoL impairment.

CDLQI is available in two versions, text only and text with cartoons. The text only version will be used in this study. The mean completion time of the text version is 120 seconds.

The purpose of the CDLQI in this study is to investigate the effects of treatment of secukinumab with respect to CDLQI at Week 12, compared to placebo, and over time up to Week 52.

This questionnaire should be completed in the language the subject is most familiar with before any other clinical assessments,

The questionnaire should be completed by the subject with the help of parent/custodian if and as needed. The site staff may help understand the questions, as necessary. The subject should be given sufficient space and time to complete the questionnaire. The study coordinator should check the questionnaire for completeness and encourage the subject to complete any missing

responses before the clinical examination. Once subjects reach 18 years of age CDLQI must no longer be completed.

The CDLQI questionnaire will be completed by the subject as indicated in [Table 6-1](#), [Table 6-2](#).

During the COVID-19 pandemic or similar major health care disruption that limits or prevents on-site study visits, CDLQI questionnaire data may be collected remotely (e.g. via telephone interview of the subject) by qualified site personnel. This will depend on local regulations, technical capabilities and following any applicable training in the required process. Documentation of the procedure should follow the vendor emergency manual directives.

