### 5.2.5 Other imputations

Only PASI and IGA mod 2011 based response variables are imputed with multiple imputation or non-response (see [Section 2.6.4](#)), other response variables (e.g. CDLQI 0 or 1 achievement) will be imputed with LOCF.

For CDLQI, CHAQ scores, missing values will be replaced by LOCF. Baseline values will not be carried forward. If no pre-treatment value exists, then values obtained after first dose of treatment can be used as baseline only if it was collected on the same day as first dose. In addition, missing baseline (PROs) values will be replaced by the means or modes of non-missing baseline values stratified by age group (<12 years or >=12 years) and sex, for continuous scale or categorical/ordinal scale, respectively.

The laboratory test values below the Lower Level of Quantification (LLQ) or above the Upper Level of Quantification (ULQ) will be imputed as LLQ or ULQ value, respectively. The numerical part of the reported result will be treated as the actual LLQ or ULQ. These laboratory values will be displayed in listings using the standard unit with the reported sign (“<” or “>”).

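### CDLQI stops at age 18 by design, but the SAP's LOCF rule has no exemption for it, so CDLQI 0/1 over time would carry pre-18 values forward for patients whom the score summaries leave out

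*SAP*

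**What the plan says.** - **Collection.** Protocol 6.6.1.1: "Once subjects reach 18 years of age CDLQI must no longer be completed". The footnote to protocol Table 6-1 agrees: "Assessment will no longer be performed once subjects reach 18 years of age".
- **Objective.** Protocol 2.2 asks for "CDLQI 0 or 1 achievement at Week 12, compared to placebo, and over time up to Week 52".
- **Scores.** SAP 2.15.1: "The summary statistics will be presented for subjects till age" under 18 years, with a figure of change from baseline in total score over time. It also plans a report restricted to assessments made under age 16: "An additional report will be created which will include only CDLQI assessments performed by subjects" below that age.
- **CDLQI 0/1.** The closing sentence of SAP 2.15.1 is "CDLQI 0 or 1 achievement will be also analyzed by visit and over time until week 104", with a reference back to SAP 2.7.3. Section 2.7.3 gives summary statistics and Fisher's exact test, but no age limit and no denominator.
- **Missing values.** SAP 5.2.5: "other response variables (e.g. CDLQI 0 or 1 achievement) will be imputed with LOCF", and for the scores, "For CDLQI, CHAQ scores, missing values will be replaced by LOCF". It bars carrying baseline values forward. It makes no exception for values absent because the patient has turned 18.

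**The concern.** These values are missing by design, at a time set by age at entry. LOCF treats them like a missed visit. A patient who turns 18 just after Week 52 would enter the Week 104 CDLQI 0/1 rate with a value about a year old, and nothing in the output would show it. If quality of life improved or worsened after that birthday, the carried value hides the change and flattens the curve.

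The score summaries take the other route and remove patients once they are 18. At a visit where both outputs are shown, they can then rest on different patients. One trend contains stale values. The other follows a group that is progressively younger at entry.

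After Week 52 the efficacy groups in SAP Table 2-1 are all secukinumab groups, so no concurrent control helps a reader separate either artefact from treatment effect.

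**Working it through.** The documents give no expected CDLQI denominator or ageing-out rate, so there is no plan figure to reproduce.

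**Inputs**
- About 160 patients aged 6 to under 18 (protocol 3.1).
- At least 30 under 12 (protocol 9.7), so at most 130 adolescents. SAP 1.1 expects 40–45 under 12, so about 115–120 adolescents; 118 is used as the central value.
- Age distribution within 12 to under 18: not given. Assumed uniform, with skewed shapes as a range.

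**Step 1: share past the 18th birthday.** With t = weeks × 7 / 365.25 years and uniform ages, the share of adolescents aged out is t/6. The share of all patients is (adolescents/160) × t/6.

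| Visit | t (years) | t/6 | 118 adolescents | 115–130 adolescents |
|---|---|---|---|---|
| Week 12 | 0.230 | 0.038 | 4.5 of 160 = 2.8% | 2.8–3.1% |
| Week 52 | 0.997 | 0.166 | 19.6 of 160 = 12.2% | 11.9–13.5% |
| Week 104 | 1.993 | 0.332 | 39.2 of 160 = 24.5% | 23.9–27.0% |

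These are shares of the age mix, not counts in the extension, because etanercept patients and placebo PASI 75 responders do not enter it. For a nominal group of 60 on one secukinumab dose (40 randomised plus 20 placebo switchers), the Week 104 share is about 14–16 patients.

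**Step 2: sensitivity to age shape at Week 104.**
- Density falling linearly with age: (t/6)² = 0.110 of adolescents, or 8.1% (118) to 9.0% (130) of patients.
- Density rising linearly with age: 1 − (1 − t/6)² = 0.554 of adolescents, or 40.9% to 45.0%.
- Overall range: about 8–45%.

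**Step 3: if LOCF is applied.** The group stays constant and the aged-out share is frozen. Under uniform ages, 19.6 of the 39.2 aged out at Week 104 had already turned 18 by Week 52. About half of the frozen values would therefore be at least a year old.

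**Step 4: if aged-out patients are dropped.** With no change in any patient, the observed rate moves by (share aged out) × (rate in stayers − rate in leavers). For illustration only, a 20-point gap gives 0.245 × 20 = 4.9 points at Week 104 and 0.122 × 20 = 2.4 at Week 52. A 10-point gap gives about 2.5 at Week 104. No gap gives zero. The documents supply no value for the gap.

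**Step 5: does the under-16 report solve it?** No. It restricts by age at assessment, so it also loses patients visit by visit. With 30 under 12 and uniform adolescent ages, about 117 are eligible at entry and about 74 at Week 104.

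**The case against.** **The under-18 limit may already cover CDLQI 0/1.** SAP 2.15.1 applies it to summary statistics, and SAP 2.7.3 describes the 0/1 output as summary statistics too. The SAP document history also records a note limiting the CDLQI summary report to patients under 18. A questionnaire that must not be given is arguably not a missing value at all. This reading is possible, but the 0/1 sentence stands apart without the limit, and SAP 5.2.5 names CDLQI 0/1 as an LOCF variable. Two programmers could build different Week 104 tables. If the limit does apply, the stale values go and the changing group takes their place.

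**The answer may lie in text not shown.** Protocol 9.4.3 breaks off at the long-term rules, and SAP 2.6.4 contains a redaction. However, SAP 5.2.5 refers to 2.6.4 for PASI and IGA responses only and sends other response variables to LOCF, so a cure there is unlikely.

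**Little is at stake.** This largely stands. About 3% age out by Week 12, randomisation is stratified by age, and CDLQI carries no alpha. The stated horizon for the scores is Week 52 (SAP Tables 1-1 and 2-10); only CDLQI 0/1 is explicitly run to Week 104. By-visit n would also show shrinkage in the score tables, although it would not show carried-forward values.

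**A stronger reading is tempting:** that the Week 104 CDLQI 0/1 trend loses its oldest adolescents and so shifts by several points. The documents do not support it. Under the LOCF rule as written nobody leaves that analysis, and any shift from dropping patients needs a leaver–stayer gap for which there is no source.

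**Conclusion.** The point holds as a fault in a stated imputation rule, of minor weight. As written, SAP 5.2.5 fills CDLQI 0/1 after the 18th birthday with a frozen pre-18 value, while SAP 2.15.1 removes the same patients from the score summaries. The descriptive within-arm trend therefore mixes treatment effect with stale values in one output and with a changing group in the other.

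The extent is about 12% of patients by Week 52 and 25% by Week 104. It rests on uniform adolescent ages and 30–45 children under 12, and the Week 104 range is about 8–45% under other age shapes. Neither the size nor the direction of any bias can be derived from the documents. A reader might infer that a sustained CDLQI 0/1 rate would be an artefact, or that the efficacy claim is weakened; neither follows. The Week 12 comparison with placebo is essentially unaffected.

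**What to change.** In SAP 5.2.5 and 2.15.1:

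1. State that LOCF is not applied to CDLQI scores or CDLQI 0/1 at any visit where the patient is 18 or older.
2. Use the same under-18 denominator for CDLQI 0/1 and the scores, and show per visit the number observed, aged out and otherwise missing.
3. Add a supportive over-time trend in the fixed group still under 18 at the last visit shown, separately for Week 52 and Week 104. Define it by age at that visit. Entry cut-offs of under 17 and under 16 would miss, because the Week 52 window runs to Day 407 (407/365.25 = 1.11 years) and the Week 104 window to Day 771 (2.11 years).
4. Keep the all-available table.

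**Cost.** Some wording, an age-at-visit flag and one extra output. Protocol 6.2.1 lists year of birth and age rather than a full birth date, but the under-18 and under-16 restrictions in SAP 2.15.1 already require age at assessment. The fixed group loses about a quarter of patients at Week 104. Under uniform ages it keeps about 117–122 of 160 (73–76%), or 44–46 of a nominal 60 per secukinumab dose group. Across the skewed shapes it keeps about 55–92% (33–55 of 60), before other dropout.
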